1.1 Study identifiers

ClinicalTrials.gov registry identifier: <https://classic.clinicaltrials.gov/ct2/show/NCT03005145>

1.2 Full Protocol Reference

The BALANCE protocol is published with open access: <https://bmjopen.bmj.com/content/10/5/e038300>
This document is the Statistical Analysis Plan Appendix to accompany the full protocol, and includes additional definitions and details.

1.3 Revision History Version

	Date	Details
1.0 (initial)	July 27, 2023	Initial version
2.0 (final)	Aug 21, 2023	Final version

2.1 Primary outcome measure

The primary outcome will be mortality at 90-days from the date of bacteremia. Although, most deaths from critical illness occur during hospital stay, lingering sequelae lead to a persistently elevated risk of death post-discharge. Therefore, we selected post-hospital 90-day mortality as a common vital status endpoint.^{1,2}

2.2 Secondary outcome measures

Secondary outcomes that we hypothesize to be non-inferior with 7d vs 14d treatment include:

- hospital mortality
- ICU mortality
- relapse rates of bacteremia with the same organism within 30 days
- ICU length of stay and ICU-free days (of 28)
- hospital length of stay and hospital free-days (of 28)
- mechanical ventilation duration and mechanical ventilation-free days (of 28)
- vasopressor duration and vasopressor-free days (of 28)

Secondary outcomes that we hypothesize to be superior with 7d vs 14d treatment include:

- antibiotic allergy and adverse events in hospital
- rates of *C. difficile* infection in hospital
- rates of secondary nosocomial infection/colonization with antimicrobial resistant organisms in hospital
- antibiotic-free days (of 28)

3. Outcome definitions

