3.2. Definitions for Secondary Outcomes

3.2.1 Hospital all-cause mortality: recorded as alive or dead at hospital discharge following index positive blood culture.

3.2.2 ICU all-cause mortality: recorded as alive or dead at index ICU discharge following index positive blood culture, among all patients diagnosed with bacteremia during ICU admission.

3.2.3 Relapse rate of bacteremia: defined as the recurrence of bacteremia due to original infecting organism (same Genus and species) within 30 days after completing course of adequate antimicrobial therapy.

3.2.4 Intensive care unit length of stay and ICU free days (of 28): ICU length of stay will be defined as the duration between ICU admission (and after the index blood culture) and discharge from the ICU for a consecutive 48-hour period. Durations will be calculated for all patients then separately for patients who died within ICU and those who did not die. ICU-free days (of 28) will be calculated as the cumulative days alive and not in ICU in the first 28 days from collection of the index blood culture; all patients who die within 28 days will be assigned 0 ICU-free days.

3.2.5 Hospital length of stay and hospital-free days of (28) – hospital length of stay will be defined as the duration between index blood culture in hospital and discharge date from hospital. Hospital-free days (of 28) will be calculated as the cumulative days alive and not in hospital in the first 28 days from collection of the index blood culture; all patients who die within 28 days will be assigned 0 hospital-free days.

3.2.6 Duration of mechanical ventilation and ventilator-free days of (28) – duration of mechanical ventilation will be defined as the number of consecutive days receiving invasive (via an endotracheal tube or tracheostomy) for any duration. Non-invasive ventilation, continuous positive airway pressure and high-flow oxygen therapy will not be considered in this analysis. Ventilator-free days (of 28) will be calculated as the cumulative days alive and not receiving invasive mechanical ventilation in the first 28 days from collection of the index blood culture; all patients who die within 28 days will be assigned 0 ventilator-free days.

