3.2.7 Duration of vasopressor use and vasopressor-free days of (28)- duration of vasopressor use will be defined as the number of consecutive days receiving intravenous vasoactive medications at any dose or any duration (e.g. epinephrine, norepinephrine, vasopressin, dopamine, phenylephrine, dobutamine, milrinone). Vasopressor-free days (of 28) will be calculated as the cumulative days alive and not receiving vasopressors in the first 28 days from collection of the index blood culture; all patients who die within 28 days will be assigned 0 vasopressor-free days.

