5.2 Analysis of secondary outcomes

Mortality rates at other time points will be calculated in a similar manner to 90-day mortality. We hypothesize that mortality rates will be non-inferior with 7 days of treatment using the same 4% non-inferiority margin, and relapse of bacteremia using a 2% absolute margin. Continuous secondary outcomes, including ICU, hospital, ventilation and vasopressor free-days by day 28 will be summarized as means and difference in means with 95% CIs as well as medians and difference in medians using quantile regression. For ICU, hospital, ventilation and vasopressor free-days by 28, a 2-day margin will be used for assessing non-inferiority.

We hypothesize that 7 days of treatment will be superior to 14 days of treatment for: antibiotic allergy and adverse events, rates of *C. difficile* infection in hospital, rates of secondary nosocomial infection/colonization with antimicrobial resistant organisms in hospital, and antibiotic-free days (of 28). The evaluation of allergy and adverse events will be important but these analyses are likely to be underpowered due to low event rates, despite the large trial sample size. Antibiotic allergy and adverse events, *C. difficile* infection and secondary nosocomial infection/colonization with antimicrobial resistant organisms are binary outcomes, and we will examine via chi-square tests of proportions. Antibiotic-free days (of 28) will be summarized as means and difference in means with 95% CIs as well as medians and difference in medians using quantile regression.

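### Four raw durations are listed as non-inferiority outcomes without a margin or a death rule, and two of them count only consecutive days (minor)

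*SAP*

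**What the plan says.** SAP section 2.2 opens its first list with "Secondary outcomes that we hypothesize to be non-inferior with 7d vs 14d treatment include". Four bullets under that heading each pair a raw duration with a free-day count. The ICU bullet reads "ICU length of stay and ICU-free days (of 28". The one for the whole admission reads "hospital length of stay and hospital free-days (of 28". Organ support is treated in the same manner: the ventilator bullet reads "mechanical ventilation duration and mechanical ventilation-free days (of 28", while the last of the four reads "vasopressor duration and vasopressor-free days (of 28".

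Section 5.2 sets the margins: 4% for mortality at the other time points, 2% for relapse and, for the day counts, "For ICU, hospital, ventilation and vasopressor free-days by 28, a 2-day margin will be used for assessing non-inferiority". The four durations get none.

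Sections 3.2.4 to 3.2.7 give 0 free-days to anyone who dies within 28 days of the index culture. They set no corresponding rule for the durations. ICU stay alone is to be shown for everyone and then by whether the patient died in the ICU.

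Ventilation duration (3.2.6) is the "number of consecutive days receiving invasive" ventilation. Vasopressor duration (3.2.7) is the "number of consecutive days receiving intravenous vasoactive medications at any dose or any duration". The matching free-days are cumulative and start at the index culture.

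**The concern.** There are two separate defects.

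**Hypothesis without a test.** A non-inferiority hypothesis with no margin cannot be tested as written, and a margin could be chosen after the data are seen. Without a death rule, a patient who dies early contributes a short duration, which reads as a good result. In a trial whose main question is whether shorter treatment costs lives, an outcome that may improve as deaths rise should not carry a non-inferiority label.

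**Unclear day count.** Counting consecutive days with no start point and no rule for a second episode leaves open which run is meant. Two programmers could derive different values from the same record, and both would miss days that the paired free-day outcome counts.

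**Working it through.** **What the plan gives.** It states no margin, standard deviation, power or expected length for any duration, so there is no duration figure to reproduce. Its mortality figures (22% baseline, 4-point margin, section 4) do reproduce: a standard non-inferiority calculation with one-sided alpha 0.025 and 80% power gives 1,684 per arm against the stated 1,686, and 2 × 1,686 × 1.05 × 1.024 = 3,625.6, which rounds up to the stated 3,626. The check below borrows the 4-point figure as an excess of deaths in the 7-day arm. Section 5.2 applies that margin to ICU and hospital mortality as well.

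**Effect of death on the two measures.** Let S and D be the mean ICU stay in survivors and non-survivors, the same in both arms. All stay lengths here are assumptions.

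- Shift in all-patient mean stay = −0.04 × (S − D)
- Shift in mean ICU-free days = −0.04 × (28 − S), taking survivors' stays to lie within the 28 days and the extra deaths to fall by day 28

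| S / D (days) | Mean stay (lower looks better) | ICU-free days (lower looks worse) |
|---|---|---|
| 12 / 6 | −0.04 × 6 = −0.24 | −0.04 × 16 = −0.64 |
| 10 / 4 | −0.04 × 6 = −0.24 | −0.04 × 18 = −0.72 |
| 16 / 7 | −0.04 × 9 = −0.36 | −0.04 × 12 = −0.48 |

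A simulation with 1,000,000 patients per arm, gamma-distributed stays and 26% against 22% mortality relaxes the first simplification, because survivors may stay beyond day 28:

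| S / D (days) | Mean stay | Free-days |
|---|---|---|
| 10 / 5 | −0.19 | −0.72 |
| 14 / 7 | −0.28 | −0.59 |
| 20 / 8 | −0.49 | −0.45 |
| 10 / 10 | 0.00 | −0.72 |
| 10 / 14 | +0.15 | −0.70 |

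The signs oppose each other only when D is below S. With equal stays the duration does not move, and with longer stays in non-survivors it moves the other way.

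**Comparison with the margin.** The largest free-day loss in these tables is 0.72 day. Free-days run from 0 to 28, so their standard deviation cannot exceed 28 / 2 = 14. With 3,626 / 2 = 1,813 per arm, the 95% half-width is at most 1.96 × 14 × √(2/1,813) = 0.91 day. Centred on the expected shift, the lower limit is −0.72 − 0.91 = −1.63, still inside −2, provided that all patients contribute.

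**Consecutive against cumulative.** Take a patient ventilated on days 1–5 and 9–20 who survives to day 28. Cumulative days are 5 + 12 = 17, giving 28 − 17 = 11 ventilator-free days. Consecutive days are 5 if the first run counts and 12 if the longest does. The duration is therefore short by 12 or 5 days relative to its partner. Mortality plays no part in this.

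**The case against.** The strongest reply is that section 5.2 already does most of the work. Without a margin there is no formal non-inferiority test, so testing is in effect confined to the free-days, and the durations fall under the general sentence on summarising continuous outcomes by means and medians. Each duration also sits beside a free-day count that penalises death, and 90-day, hospital and ICU mortality are tested directly. This stands as a limit on the consequence. It does not remove the mismatch: section 2.2 still states a non-inferiority hypothesis that section 5.2 cannot test. The ICU split by death in 3.2.4 is useful description, but it conditions on an event after randomisation, and the all-patient figure remains.

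A second reply also stands: the direction is not established. The SAP gives no durations by survival status, and the arithmetic covers ICU stay only. Section 5.3 shows that non-ICU patients are enrolled, and 3.2.4 computes ICU durations for all patients without saying how those never in an ICU are scored. If they count as 0, and if 50% of survivors and 80% of non-survivors were ever in an ICU (an assumption), the 12/6 pair becomes 6.0/4.8 and shifts by −0.04 × 1.2 = −0.05 day. The 16/7 pair becomes 8.0/5.6 and shifts by −0.04 × 2.4 = −0.10 day. For ventilation and vasopressors, enough survivors at 0 could reverse the sign.

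A reader might also infer that counting consecutive days favours the arm with more deaths. It does not follow: missing a later episode has no inherent link to mortality.

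**Conclusion.** The point holds as a minor one. Sections 2.2 and 5.2 disagree on which day-count outcomes are non-inferiority outcomes, the four durations have no death rule, and two have an ambiguous day count.

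For a 4-point excess of deaths, the truncation effect on mean ICU stay is under 0.5 day. It rests on assumed stay lengths and on non-survivors having shorter stays than survivors. A reader might infer that the plan would produce two contradictory non-inferiority findings for one resource. The figures do not support that: the free-day loss of about 0.45 to 0.72 day is within the 2-day margin, and a duration with no margin has no verdict to contradict. What is shown is an opposite sign. Nor do the documents show that all four durations would move in the reassuring direction.

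The undercount of restarted support is a measurement error in its own right. The primary outcome, its margin and the sample size are unaffected.

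**What to change.** - **Section 2.2:** keep only the four free-day outcomes as non-inferiority hypotheses, with the 2-day margin of section 5.2.
- **Sections 2.2, 3.2.4 to 3.2.7 and 5.2:** list the four durations as descriptive, shown overall and by survival status for all four. State that no non-inferiority claim is made from them and no causal claim from the survival split. Say how patients who never received the support, or never entered an ICU, are scored.
- **Sections 3.2.6 and 3.2.7:** define duration as cumulative days on support from the index culture over a stated window, so that repeat episodes count.

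The cost is wording; no new margin is needed. Four secondary outcomes lose a non-inferiority label. A 28-day window would drop later support days and, in 28-day survivors, make the duration simply 28 minus the free-days. A longer window would avoid that if support days are recorded beyond day 28.

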3.1. Primary Outcome Definition

The primary outcome will be mortality (from any cause) at 90-days from the date of bacteremia, defined by vital status at 90 days from the date of collection of the index positive blood culture.

3.2. Definitions for Secondary Outcomes

3.2.1 Hospital all-cause mortality: recorded as alive or dead at hospital discharge following index positive blood culture.

3.2.2 ICU all-cause mortality: recorded as alive or dead at index ICU discharge following index positive blood culture, among all patients diagnosed with bacteremia during ICU admission.

3.2.3 Relapse rate of bacteremia: defined as the recurrence of bacteremia due to original infecting organism (same Genus and species) within 30 days after completing course of adequate antimicrobial therapy.

3.2.4 Intensive care unit length of stay and ICU free days (of 28): ICU length of stay will be defined as the duration between ICU admission (and after the index blood culture) and discharge from the ICU for a consecutive 48-hour period. Durations will be calculated for all patients then separately for patients who died within ICU and those who did not die. ICU-free days (of 28) will be calculated as the cumulative days alive and not in ICU in the first 28 days from collection of the index blood culture; all patients who die within 28 days will be assigned 0 ICU-free days.

3.2.5 Hospital length of stay and hospital-free days of (28) – hospital length of stay will be defined as the duration between index blood culture in hospital and discharge date from hospital. Hospital-free days (of 28) will be calculated as the cumulative days alive and not in hospital in the first 28 days from collection of the index blood culture; all patients who die within 28 days will be assigned 0 hospital-free days.

3.2.6 Duration of mechanical ventilation and ventilator-free days of (28) – duration of mechanical ventilation will be defined as the number of consecutive days receiving invasive (via an endotracheal tube or tracheostomy) for any duration. Non-invasive ventilation, continuous positive airway pressure and high-flow oxygen therapy will not be considered in this analysis. Ventilator-free days (of 28) will be calculated as the cumulative days alive and not receiving invasive mechanical ventilation in the first 28 days from collection of the index blood culture; all patients who die within 28 days will be assigned 0 ventilator-free days.

3.2.7 Duration of vasopressor use and vasopressor-free days of (28)- duration of vasopressor use will be defined as the number of consecutive days receiving intravenous vasoactive medications at any dose or any duration (e.g. epinephrine, norepinephrine, vasopressin, dopamine, phenylephrine, dobutamine, milrinone). Vasopressor-free days (of 28) will be calculated as the cumulative days alive and not receiving vasopressors in the first 28 days from collection of the index blood culture; all patients who die within 28 days will be assigned 0 vasopressor-free days.

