The primary analysis will assess whether 7 days of treatment is associated with a non-inferior 90-day mortality rate in comparison to 14 days of treatment. We require 1,686 patients per arm to establish a non-inferiority margin of +4% absolute increase in mortality (baseline mortality 22%)⁵ power 80%, alpha 0.025, one-sided equivalence test). We have inflated this to account for a maximum of 5% loss-to-follow-up, and have incorporated early stopping rules to account for the 3 interim analyses (coefficient 1.024)^{6,7} for a total sample size of 3626. Recent landmark trials in with similar baseline mortality rates have used +4% as a non-inferiority margin;^{8,9} the U.S. FDA has recommended a similar margin for analogous industry-sponsored trials.¹⁰ The PneumA study of 8 vs 15 day treatment for VAP used a non-inferiority margin of 10%,¹¹ as have other recent prominent infectious diseases non-inferiority trials,^{12,13} but we believe lower non-inferiority margins are desirable, when feasible, for the outcome of mortality.

5. Statistical analysis

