5.3 Subgroup analyses

The main subgroup analysis will be based on the underlying infectious syndrome causing bacteremia (vascular catheter-related, pneumonia, pyelonephritis, intra-abdominal, skin and soft tissue, other identified source, or

unknown source). We will also perform subgroup analyses based on ICU versus non-ICU enrolments, community- versus hospital-acquisition (>48h post admission), Gram positive versus Gram negative infection, illness severity (APACHE II score of ≥ 25 vs. < 25), vasopressor use on day of randomization and baseline Clinical Frailty Score (≥ 5 vs. < 5).¹⁸ We hypothesize that the non-inferiority of 7 versus 14 days of treatment will be consistent across these subgroups. The subgroup analyses will only be conducted for the primary outcome.

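### The ICU-mortality set does not require patients to be in ICU at randomisation, so any who had already left the index ICU alive pull this secondary test towards non-inferiority

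*SAP*

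**What the plan says.** ICU mortality is listed in SAP section 2.2 among the secondary outcomes expected to be non-inferior with 7 days of treatment. Section 3.2.2 gives both the event and the population: "recorded as alive or dead at index ICU discharge following index positive blood culture, among all patients diagnosed with bacteremia during ICU admission". The date of randomisation enters neither part.

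Section 5.2 says how mortality outcomes other than the primary one are judged: "We hypothesize that mortality rates will be non-inferior with 7 days of treatment using the same 4% non-inferiority margin". The margin is an absolute difference in proportions.

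Two other places bear on the point. Section 5.3 plans a comparison by ICU status: "We will also perform subgroup analyses based on ICU versus non-ICU enrolments". It does not define an ICU enrolment, but in the same list it uses the day of randomisation as the reference for vasopressor use. Section 5.1 plans a modified intention-to-treat analysis of the primary outcome that drops deaths before day 7 of treatment, because those deaths come before the two arms differ.

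**The concern.** A patient can have the index culture drawn and bacteremia diagnosed in ICU, move to the ward, and then be randomised. Under section 3.2.2 that patient belongs to the ICU-mortality set, although the outcome (alive at index ICU discharge) was fixed before allocation and cannot respond to treatment duration.

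In a superiority trial such patients would cost power. In a non-inferiority test on an absolute margin they act the other way: they reduce any real difference while the margin stays put, so a harmful excess is more easily declared acceptable. Section 5.1 recognises that outcomes settled before the arms diverge carry no information about duration, but acts on this only for early deaths in the primary outcome. For ICU mortality there is no counterpart, and the SAP does not ask for the number of patients affected to be reported.

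**Working it through.** **1. The plan's own figure.** The SAP gives no sample size for ICU mortality. The figure that uses the 4-point margin is the primary one in section 4, with 22% baseline mortality and "power 80%, alpha 0.025, one-sided equivalence test":

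n per arm = 2 × 0.22 × 0.78 × (1.960 + 0.842)² / 0.04² = 1,684, against 1,686 stated.

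Total = 2 × (1,686 × 1.024 × 1.05, rounded up) = 2 × 1,813 = 3,626, as stated.

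The plan's arithmetic reproduces, so the same test can be used below.

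**2. Who is in the set.** Entry: "among all patients diagnosed with bacteremia during ICU admission". Event: "recorded as alive or dead at index ICU discharge following index positive blood culture". Neither condition fails for a patient whose index ICU discharge came before randomisation.

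**3. Dilution.** Let f be the fraction of the set, equal in expectation between arms, who left the index ICU alive before randomisation. Let p be ICU mortality in the 14-day arm and d the true excess with 7 days, both among patients still in ICU at randomisation. Then:

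- 14-day arm over the whole set: (1−f) × p
- 7-day arm over the whole set: (1−f) × (p + d)
- apparent difference: (1−f) × d
- true excess that appears as exactly 4 points: 4 / (1−f)

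| f (assumed) | A true 4.0 points appears as | True excess that appears as 4.0 |
|---|---|---|
| 0 | 4.0 | 4.0 |
| 10% | 3.6 | 4.4 |
| 20% | 3.2 | 5.0 |
| 30% | 2.8 | 5.7 |

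**4. Effect on the error rate.** This needs further assumptions, none of them in the SAP: ICU mortality of 22% among those still at risk (borrowed from the primary baseline), a true excess of exactly 4 points among them, a one-sided 0.025 test, and the number of ICU-diagnosed patients per arm. With the normal approximation,

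P(declare non-inferiority) = Φ[(0.04 − (1−f)d) / SE − 1.960], where SE is the unpooled standard error of the diluted proportions.

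Example with f = 20% and 843 per arm (half of 1,686): the proportions are 0.176 and 0.208, SE = 0.0192, and Φ(0.008/0.0192 − 1.960) = 6.1%.

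| f | 506 per arm | 843 per arm | 1,686 per arm |
|---|---|---|---|
| 0 | 2.5% | 2.5% | 2.5% |
| 10% | 3.6% | 3.9% | 4.7% |
| 20% | 5.1% | 6.1% | 8.5% |
| 30% | 7.4% | 9.7% | 15.2% |

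**5. What restriction costs.** Limiting the set to patients in ICU at randomisation returns the error to 2.5% in this model, but leaves fewer patients. Starting from 843 per arm with the arms truly equal, the chance of showing non-inferiority changes from 54% to 47% (f = 10%), from 58% to 43% (20%) and from 62% to 38% (30%). Part of the higher figure in each pair comes from the dilution itself. These figures count no patients added by the new definition.

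**The case against.** **The harm is conditional.** The SAP gives neither f nor the interval from diagnosis to randomisation. Timing of enrolment is normally left to the protocol, which is not at hand. If patients are randomised while still in ICU, f is near 0 and nothing is lost. This stands: the values of 10% to 30% are illustrations. It limits the size of the point, but the stated rule still admits such patients and sets no check on their number.

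**The comparison is valid as randomised.** Place of diagnosis is fixed before allocation, so the arms stay balanced, and anchoring on the index culture matches the primary outcome and the 28-day outcomes. This also stands. The problem is reduced ability to detect a difference; there is no selection bias.

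**A conflict with section 5.3.** A reader might infer that the ICU subgroup and the ICU-mortality set describe different patients. The SAP does not establish this: it does not define an ICU enrolment, and if enrolments were classified by ICU status at diagnosis the two sets would coincide. A mismatch is possible, no more.

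**Patients cultured before ICU admission.** A reader might also infer that patients cultured on the ward or in the emergency department and randomised in ICU are excluded. That depends on equating diagnosis with culture collection. If the positive result during the ICU stay counts as diagnosis, they are included. Hospital mortality and ICU-free days carry no place-of-diagnosis restriction and would cover them in any case.

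**The remedy is incomplete.** Patients who leave ICU after randomisation but before the arms diverge at day 7 also carry no treatment contrast, and restricting to patients in ICU at randomisation keeps them. This is correct.

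**Conclusion.** The point holds in a limited form. Section 3.2.2 admits patients whose ICU outcome was settled before allocation. Every such patient reduces the absolute difference that section 5.2 judges against a fixed 4-point margin, and the direction favours non-inferiority.

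The size cannot be given from the SAP. The factor is (1−f), which assumes only that f is the same in both arms, as randomisation ensures in expectation. The error rates above rest in addition on an assumed ICU mortality, test level and number of ICU patients. A reader might conclude that the ICU-mortality result will be materially diluted; the document does not support that, because nothing in it shows that such patients exist in material number.

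The point concerns one secondary outcome for which no power is claimed. It does not touch the 90-day primary outcome. It is still worth correcting, because the direction is anti-conservative and the correction should be cheap.

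**What to change.** Redefine ICU mortality in section 3.2.2 as death before discharge from the ICU stay in progress at randomisation, among all patients in ICU at randomisation, wherever the index culture was collected. State in section 5.3 whether an ICU enrolment means the same thing.

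If the current definition is kept, at minimum:

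- pre-specify the analysis above beside it;
- report, by arm, how many index ICU discharges preceded randomisation;
- say whether diagnosis means the date of culture collection or of the positive result.

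The cost is SAP wording. The dates of randomisation and ICU discharge, and ICU status at enrolment, should already be held, since sections 3.2.2, 3.2.4 and 5.3 rely on ICU discharge and enrolment status. If f is above 0, the set is smaller and the confidence interval wider, partly offset by any patients cultured before ICU admission who are added. Because the fix leaves in those who leave ICU between randomisation and day 7, the report should acknowledge that some dilution remains.
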